Design: Patients are studied after 4 weeks of oral 3-OHB three times daily (36 g "Perfect Keto Base" or 25g HVMN Ketone Ester depending on the outcome of KETO-KINETICS three times) and 4 weeks isocaloric placebo-drink. Both "Perfect Keto Base" (Perfect Keto, Glendale Heights, IL, USA) and HVMN Ketone Ester (HVMN, San Francisco, CA, USA) are a commercially available ketone diet supplements.

Endpoints: 1) Cardiac output (primary), mixed venous saturation (SVO2), pulmonary wedge pressure 2) Rest/Peak Exercise Echocardiography (LVEF, Global Strain), 3) Cardiopulmonary exercise test, 4) Whole-body substrate metabolism, insulin signalling and lipolysis.

Methods: Swan-Ganz monitoring, echocardiography, exercise capacity, whole-body glucose, FFA and protein metabolism will be examined using isotope tracer techniques. Furthermore, muscle biopsies will be drawn for studies of insulin signalling and lipolysis (chapter 5).

[figure not shown]

Figure 1: Patient Inclusion flowchart

Table 1: Study Visits Overview

Visit	V0 Screening	Teleph. Contact	V1 Randomizat ion	V2 Hemodynamic examination 1	V3 Metabolic Examinations 1	V4 Hemodynamic examinations 2	V5 Metabolic Examinations 2
Time (Days, Weeks, Months)	-4W to 0	-3½ W-0W	0	3-5W	3-5W	10-12W	10-12W
General							

Original protocol title: *Modulation of circulating levels of the ketone body 3-hydroxybutyrate in patients with chronic heart failure: Cardiovascular and metabolic effects*

[name], Læge, PhD-studerende, Afd. for Hjertesygdomme, Aarhus Universitetshospital Skejby, Aarhus, Denmark
Scientific Committee ref.: 1-10-72-362-18

Informed consent	X						
In-and exclusion criteria	X		X				
Relevant medical/surgical history			X				
Relevant concomitant medication (1)			X				
Randomize patient			X				
Study medication							
Delivery	(Trial period)		X				
Crossover					X		
Clinical assessment							
NYHA class			X	X	X	X	X
Height			X				
Weight			X	X	X	X	X
Echocardiography				X		X	
Swan-Ganz Monit.				X		X	
CPX-test				X		X	
Whole-Body Metabolism					X		X
Blood Samples				X	X	X	X
Muscle Biopsies					X		X
ECG			X	X		X	
Blood pressure, heart rate	X		X	X	X	X	X
Safety							
Reporting of: -Endpoints -SUSARs -selected AEs		X	X	X	X	X	X

Table 2: Hemodynamic study day overview

Time	07.30	08.30	09.15	09.30	10.30	10.50	11.10	11.30	12.30
Arrival			X						
Swan Ganz				X					
Exercisetest						X			
Blood Samples				X		X	X	X	X
Echocardiography				X		X	X	X	X
Invasive measurements				X		X	X	X	X

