Original protocol title: *Modulation of circulating levels of the ketone body 3-hydroxybutyrate in patients with chronic heart failure: Cardiovascular and metabolic effects*

[name], Læge, PhD-studerende, Afd. for Hjertesygdomme, Aarhus Universitetshospital Skejby, Aarhus, Denmark
Scientific Committee ref.: 1-10-72-362-18

3-OHB/placebo ingestion	x
End of study day	x

Table 3: Metabolic study day overview

Time	07.30	08.30	09.30	10.30	11.30	12.30	13.30	14.30
Arrival		x						
Basal period								
3-OHB sipping								
3-OHB sipping + Clamp								
[3- ³ H]Glucose-Infusion								
[9,10- ³ H]Palmitate-infusion								
Muscle Biopsy			x					x
Blood samples	x		x	x	x	x	x	

5 Methods

5.1.1 Swan-Ganz Monitoring:

This is a standard procedure at the clinical research site and will be performed in a dedicated cardiac catheter lab with experienced physicians. Standard triple-lumen Swan-Ganz thermister and balloon-tipped catheters will be used. Catheters will be introduced using the internal jugular vein, using ultrasound guidance, and advanced using pressure waveform and fluoroscopy into the pulmonary artery. Cardiac output will be measured using the thermodilution method.

Measurements will be made at rest, during peak exercise and post-exercise.

5.1.2 Rest/Peak Exercise Echocardiography:

We intend to use a GE VIVID 7 or 9E system (GE Medical System, Horten, Norway) with a 2.5-MHz transducer for transthoracic echocardiography. For image analysis EchoPAC (GE-Vingmed Ultrasound, Horten, Norway) will be used. All measurements will be the averaged over 3 consecutive heart cycles in end-expiration. 2D echocardiography will be performed according to national guidelines [14]. In case of poor image quality, a contrast agent (SonoVue/Optison) will be used to opacify the left ventricle (LV) [15, 16]. Regarding LV measurements, the following parameters will be recorded: 2D [16], regional wall motion score (16 segment model), LVEDV and LVESV, left atrial volume, tissue Doppler study of the mitral annulus and LV strain and strain-rate[17].

5.1.3 Whole-body metabolism:

Glucose metabolism is determined by isotope dilution technique with constant infusion of [3-³H] glucose (12 µCi / min) from two hours before and 60 minutes after intake of ketones or isocaloric placebo.

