5.1.4 Muscle biopsies

Samples are taken from the vastus lateralis by sterile technique. Proteins involved in insulin-signalling and lipolysis will be determined by Western Blot technique.

5.1.5 Cardiopulmonary Exercise Test:

Cardiopulmonary exercise capacity will be performed using a staged bicycle exercise test with measurements of oxygen consumption and carbon dioxide excretion. After resting measurements are obtained patients will start exercising at 0 watts and using 3 minute intervals increase to 20 watts and then with 10 watt increments every 3 minutes until peak exercise (Borg > 18). At each level of exercise hemodynamic and echocardiographic measurements will be recorded. A preliminary exercise test will be performed prior to the baseline study to make the patient familiar with the procedure.

5.1.6 Blood samples:

Venous blood samples for measurements of plasma insulin, free fatty acids, glucose, ketone bodies, lactate, haemoglobin, P-Na⁺, P-K⁺. Will be measured three times during each visit P-LDL, P-HDL and P-Cholesterol (total), prostaglandin E2, I2, F2 α , thromboxane A, erythropoietin, thrombopoietin and granulocyte stimulating factor will be measured twice during the pilot study and the hemodynamic study days.

6 Power calculation and statistics

Power calculations

In the pilot study we plan to include 8 patients. However, if necessary because of drop-outs or missing values up to 10 patients will be included.

Coefficiency of variation (CV) regarding Cardiac output by pulmonary artery catherization is determined to be 4 % [19]. By enrolling 8 patients in the KETO-KINETIC pilot study, we will be able to detect a relative difference of 6% with a power of 90% and a two-sided significance level of 5%. In the KETO-CHF study by enrolling 20 patients in the hemodynamic examinations, and allowing up to 20 % missing values, we will be able to determine a relative difference of 4 %, and thus detect changes related to clinical outcome [20], with a power of 90% and a two-sided significance level of 5%.

In the metabolic studies, previous studies have shown an SD of the difference of 8% and an effect size of 10%. With power and significance level as described above a sample size of 8 patients are needed. To allow 20% missing values 10 patients will be included in the metabolic studies.

Reporting of endpoints:

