For these studies normally distributed variables will be presented as mean \pm SD. Non-parametric statistics and appropriate log-transformation will be performed if assumption of normality is not met. A two-tailed p value of 0.05 or less will be considered statistically significant.

Differences will be compared by appropriate paired statistical tests. Regression analysis will be performed and correlation coefficients will be presented when appropriate.

7 Patient recruitment

Patients with stable HF will be recruited from the outpatient HF clinic at Aarhus University Hospital.

Inclusion criteria: Chronic HF: NYHA class II-III, left ventricular ejection fraction (LVEF) <40%

Exclusion Criteria: Diabetes or HbA1c >48 mmol/mol, significant cardiac valve disease, severe stable angina pectoris, severe comorbidity as judged by the investigator, inability to give informed consent

Original protocol title: *Modulation of circulating levels of the ketone body 3-hydroxybutyrate in patients with chronic heart failure: Cardiovascular and metabolic effects*

[name], Læge, PhD-studerende, Afd. for Hjertesygdomme, Aarhus Universitetshospital Skejby, Aarhus, Denmark
Scientific Committee ref.: 1-10-72-362-18

Recruitment and informed consent

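### Does leaving open which cardiac output reading is primary in KETO-CHF call for a change to the plan?

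*Combined protocol and SAP*

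**What the plan says.** Section 4 describes KETO-CHF as a randomised double-blind crossover in 20 patients. Its first endpoint group is "Cardiac output (primary), mixed venous saturation (SVO2), pulmonary wedge pressure". Echocardiography is listed separately and labelled as both resting and peak exercise. The cardiopulmonary exercise test has its own item. Cardiac output carries no such label.

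Section 5.1.1 says cardiac output is measured by thermodilution, then adds: "Measurements will be made at rest, during peak exercise and post-exercise". Table 2 has a row for "Invasive measurements" marked at several times of the study day, and a row for "3-OHB/placebo ingestion". Section 5.1.5 says of the exercise test: "At each level of exercise hemodynamic and echocardiographic measurements will be recorded".

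In section 6, the power text gives a single coefficient of variation, "regarding Cardiac output by pulmonary artery catherization is determined to be 4" per cent, and a single detectable difference of 4% for KETO-CHF, with no exercise state. The reporting text says "Differences will be compared by appropriate paired statistical tests" and "A two-tailed p value of 0.05 or less will be considered statistically significant".

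**The concern.** A paired test needs one number per patient per period. The protocol collects cardiac output in at least three states, and no section in the endpoint, power or statistics text says which reading enters the primary test or how several would be combined. Resting and peak-exercise cardiac output answer different questions. Because the study product or placebo is also taken on the haemodynamic day, the timing of a reading relative to that intake could matter for interpretation too.

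If the reading were picked after the data were seen, the stated two-sided 5% level would no longer be secured. A reader could not tell from the protocol whether a positive result concerned rest or exercise. In a 20-patient trial with one named primary endpoint, that looks like a serious omission.

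**Working it through.** **Inputs from the documents.** 20 patients with up to 20% missing gives 20 × 0.80 = 16 evaluable. The coefficient of variation is 4%, the detectable difference 4%, power 90%, two-sided level 5% (section 6). There are three states: rest, peak and post-exercise (section 5.1.1).

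**The plan's own power figure.** Section 6 does not say whether the 4% describes one reading or the paired difference, so both are tried with a paired t test, n = 16, 15 degrees of freedom. The noncentrality is (difference / SD of difference) × √n.

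| SD of difference | Noncentrality | Power for 4% | Detectable at 90% power |
|---|---|---|---|
| 4% | 4/4 × 4 = 4.00 | 96% | 3.47% |
| √2 × 4% = 5.66% | 4/5.66 × 4 = 2.83 | 75% | 4.91% |

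Neither gives exactly 90%, and the stated figure lies between them. That is a separate sample-size matter. For the present question, the calculation as stated has the form of one comparison of one quantity, with no division of the 5% level.

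**False-positive risk if any of three states could count.** This is a hypothetical rule; the plan does not contain it. For independent readings the risk is 1 − 0.95³ = 14.3%. For equally correlated readings, simulated paired t tests with n = 16 give the following (two simulation runs; correlations assumed):

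| Assumed correlation | Risk |
|---|---|
| 0.5 | 12.6% to 12.7% |
| 0.7 | 11.0% to 11.1% |
| 0.9 | 8.5% to 8.7% |

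Readings on one day in one patient are probably well correlated, so the lower values are the more plausible.

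**Risk if one state is named in advance.** One test at 0.05 has a 5% risk, whether the state is rest, peak or post-exercise. The error rate therefore depends on when the choice is made, not on which state is chosen.

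**Keeping three co-primaries with a Bonferroni split.** At 0.05/3 = 0.0167 per reading, power for 4% falls from 96% to 89% (SD 4%) or from 75% to 57% (SD 5.66%). That costs power to solve a problem that a single reading does not have.

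**Which reading the text points to.** Exercise is labelled where it is meant in the endpoint list (echocardiography, the exercise test), and cardiac output is left plain. The power text uses one variability figure and one difference. Together these suggest a single comparison, probably at rest. They do not prove it, because section 5.1.1 applies all three states to the catheter readings.

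**What is left out of the count.** Section 5.1.5 speaks of haemodynamic readings at each workload but does not name cardiac output. The Table 2 times overlap the three states and are not additional to them. The time of the ingestion row cannot be read in the text available for this review, so nothing is concluded about readings before or after intake.

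**The case for a change.** The strongest case for a change is that the wording really is silent. The inference to rest relies on a missing label and a single variability figure, while the hypothesis and the third objective name both cardiac function and exercise capacity. Double blinding does not stop anyone choosing a reading after the code is broken; only advance specification does. Even at a correlation of 0.9, an any-of-three rule would give 8.5% to 8.7%, about 1.7 times the nominal 5%. Naming the reading would take a sentence.

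Most of this stands as description: the definition is absent from this document, and the arithmetic is right for the rule assumed. It does not show that the plan prescribes a faulty analysis. The inflation comes entirely from a success rule, or an after-the-fact choice, that no section proposes. Nor does it identify a better method: several definitions would be acceptable, and the remedy would be to record whichever one the investigators intend. The concern about intake timing is narrower still: the endpoint text does not link the reading to that day's intake, but whether the table already makes the order plain cannot be judged here.

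**Conclusion.** The gap is real but is one that analysts fill sensibly, and no change to the plan follows. Section 6 is built around one paired comparison of cardiac output. Carried out that way on one reading settled before unblinding, the test keeps its 5% level. The figures of about 9% (correlation 0.9) to 14% (independence) for three states bound a hypothetical worst case; they rest on an any-of-three rule the plan does not state and on assumed correlations. The conclusion assumes that the investigators settle the reading before the treatment code is broken and treat the other states as supportive. It is limited to the text available, since Figure 1 and some pages could not be seen. When the results are read, the one thing to check is that the reported primary states its exercise state and its timing relative to the study-day intake.

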5.1.4 Muscle biopsies

Samples are taken from the vastus lateralis by sterile technique. Proteins involved in insulin-signalling and lipolysis will be determined by Western Blot technique.

5.1.5 Cardiopulmonary Exercise Test:

Cardiopulmonary exercise capacity will be performed using a staged bicycle exercise test with measurements of oxygen consumption and carbon dioxide excretion. After resting measurements are obtained patients will start exercising at 0 watts and using 3 minute intervals increase to 20 watts and then with 10 watt increments every 3 minutes until peak exercise (Borg > 18). At each level of exercise hemodynamic and echocardiographic measurements will be recorded. A preliminary exercise test will be performed prior to the baseline study to make the patient familiar with the procedure.

5.1.6 Blood samples:

Venous blood samples for measurements of plasma insulin, free fatty acids, glucose, ketone bodies, lactate, haemoglobin, P-Na⁺, P-K⁺. Will be measured three times during each visit P-LDL, P-HDL and P-Cholesterol (total), prostaglandin E2, I2, F2 α , thromboxane A, erythropoietin, thrombopoietin and granulocyte stimulating factor will be measured twice during the pilot study and the hemodynamic study days.

6 Power calculation and statistics

Power calculations

In the pilot study we plan to include 8 patients. However, if necessary because of drop-outs or missing values up to 10 patients will be included.

Coefficiency of variation (CV) regarding Cardiac output by pulmonary artery catherization is determined to be 4 % [19]. By enrolling 8 patients in the KETO-KINETIC pilot study, we will be able to detect a relative difference of 6% with a power of 90% and a two-sided significance level of 5%. In the KETO-CHF study by enrolling 20 patients in the hemodynamic examinations, and allowing up to 20 % missing values, we will be able to determine a relative difference of 4 %, and thus detect changes related to clinical outcome [20], with a power of 90% and a two-sided significance level of 5%.

In the metabolic studies, previous studies have shown an SD of the difference of 8% and an effect size of 10%. With power and significance level as described above a sample size of 8 patients are needed. To allow 20% missing values 10 patients will be included in the metabolic studies.

Reporting of endpoints:

For these studies normally distributed variables will be presented as mean \pm SD. Non-parametric statistics and appropriate log-transformation will be performed if assumption of normality is not met. A two-tailed p value of 0.05 or less will be considered statistically significant.

Differences will be compared by appropriate paired statistical tests. Regression analysis will be performed and correlation coefficients will be presented when appropriate.

7 Patient recruitment

Patients with stable HF will be recruited from the outpatient HF clinic at Aarhus University Hospital.

Inclusion criteria: Chronic HF: NYHA class II-III, left ventricular ejection fraction (LVEF) <40%

Exclusion Criteria: Diabetes or HbA1c >48 mmol/mol, significant cardiac valve disease, severe stable angina pectoris, severe comorbidity as judged by the investigator, inability to give informed consent

Original protocol title: *Modulation of circulating levels of the ketone body 3-hydroxybutyrate in patients with chronic heart failure: Cardiovascular and metabolic effects*

[name], Læge, PhD-studerende, Afd. for Hjertesygdomme, Aarhus Universitetshospital Skejby, Aarhus, Denmark
Scientific Committee ref.: 1-10-72-362-18

Recruitment and informed consent

Study participants will be recruited from the participating centres. Participants will receive oral and written information regarding the study together with the brochure: " Volunteer's rights in a health science research project" ("Forsøgspersoners rettigheder i et sundhedsvidenskabeligt forskningsprojekt") and an agreement form requesting accept to be contacted by the investigators for further information. Interested subjects will have to sign the enclosed agreement form and return it before being contacted. Subjects agreeing to receive further information will be contacted by phone. The subjects are informed about the project's background, objectives, methods, risks, side effects, disadvantages, benefits and potential usefulness, and that there may be unforeseen risks and impacts of participation in the project. The subjects are informed that participation is voluntary and that he / she at any time without reason can withdraw their consent and drop out of the project without any consequences for their future treatment. The information is repeated orally upon arrival for the screening visit. The subjects will have the opportunity to ask questions and to bring a companion at this visit. The information conversation will take place in privacy in an investigation room at Department of Cardiology, Aarhus University Hospital and carried out by any of the investigators. Before signing the consent form, the participant will have the opportunity to re-consider for at least 24 hours. Copies of participant information and consent form will be given to the subjects. No study-related examinations will be conducted until after the informed consent form has been signed. The investigator will ensure that the participant is adequately informed both orally and written about the study, background, design, risks, side effects, disadvantages, benefits and usefulness. The investigators are responsible for ensuring obtained written informed consent from all subjects before enrolment in the study.

Information on individual medical data will be given by a medical doctor affiliated with the study. However, the individual subject's desire not to know his or her own data will be respected.

By participating in the study, subjects agree that relevant information from medical records that potentially can influence on the study may be passed to the responsible investigators. This may be information relating to medicine intake and previous and current diseases and treatments.

8 Data collection and processing

Data collection and processing will be carried out in accordance with current legislation on processing of personal data, and the general data protection regulation.

Source data will be recorded in the patient's electronic patient record or on specific worksheets. Invasive hemodynamics and echocardiographic data will be stored at the Department of Cardiology Aarhus University Hospital. A centralized electronic Case Report Form (CRF) will be constructed for data capture. Data will be stored in coded form in 15 years according to recommendations from the Data Monitoring Board. After which it will be transmitted to the Danish Data Archives.

Biobanks

A research biobank will be established at Department of Endocrinology and Metabolism, Aarhus University Hospital. This research biobank will store blood samples in coded form for later analysis (>7 days). Blood samples will be stored at -80°C. After completion of the project, excess biological material (blood plasma and muscle biopsies) will be transferred to a biobank for future research. This biobank will be registered separately with the Central Denmark Region.

9 Patient discomfort and risks

The enrolled volunteers should expect to spend approx. 1 hour at the screening visit and 6-8 hours at each study visits. Participants will have their travel expenses from participating in the project reimbursed. In case of injury, patients are covered under The Patient Compensation Association.

Blood samples (all studies)

The studies will require venous puncture which may inflict a short pain and a risk of a small hematoma. There is a minimal risk for infection by the point of insertion. A total of 340 mL of blood will be drawn for the KETO-KINETICS study distributed over the three study days. In the KETO-CHF 110 mL of blood will be drawn at each visit. This should cause no side effects.

Radiation

The risk for adverse health effects from cancer is proportional to the amount of radiation dose absorbed and strongly dependent on age. When reviewing the numbers below, the natural incidence of fatal cancer in Denmark of about 25% and the 5-year mortality of 43% in Danish heart failure patients [2] should be taken into account. Radiation doses for the KETO-KINETICS and Keto-CHF study is 6 mSv and 4 mSv each respectively, corresponding to IRCP category IIb. Thus, participation in one study increases cancer risk from 25% to 25.02% in the KETO-CHF study and 25.03% in the KETO-KINETICS study.

Right heart catheterization

This method has been implemented at our centre for decades both in daily practice and for research use. The applied local anaesthetic, may cause a short stinging pain (few seconds) and in some cases cause temporally hoarseness (1-2 hours). Catheter placement through the internal jugular vein will be performed under sterile conditions. The catheter will be advanced to the pulmonary artery for measurements of pressure and cardiac output. Accidental puncture of the carotid artery will be avoided by transcutaneous ultrasound guidance. A single dose of antibiotics will be given when appropriate (pacemakers, artificial valves, etc). At the puncture site of the neck, a small hematoma can appear which does not require any further treatment. The procedure will be performed by experienced physicians, and according to the guidelines from the Danish Society of Cardiology the complication rate is described as particularly low. Brief periods of atrial fibrillation or self-limiting ventricular arrhythmias are the most common. There are reports of right atrial or right ventricle perforation using stiff catheters, but no such episodes were reported using balloon tipped catheters. Such balloon tipped catheters will be applied in the present project. In a study of 7218 patients undergoing right heart catheterization, a fatal episode related to the procedure was described in one patient due to rupture of a pulmonary artery [21]. This patient had severe pulmonary hypertension but no HFrEF. Thus, a patient category with a completely different disease located in the pulmonary vessels. No such patients will be enrolled in the present study. Finally, it should be mentioned that the method is applied in an ongoing trial (TEMPO) at Dept. of Cardiology Aarhus University, and in a recent published study in which healthy Danish volunteers were investigated, and no adverse events were reported [22].

Echocardiography

Echocardiography uses standard ultrasound techniques to image the heart. It is performed with the patient in the left lateral position and is without risk or discomfort for the patient.

Muscle biopsies

During the metabolic examination days two muscle biopsies will be drawn. A local anaesthetic will be used to minimize patient discomfort. After the biopsy, a hematoma will develop as well as soreness of the muscle. In rare cases a local infection may occur. No patients on oral anticoagulant treatment will be subjected to this procedure.

Adverse Effects of study medication

Ketone supplements may cause mild gastrointestinal discomfort and mild headaches in the first days entering a regimen. Patients are therefore subjected to a four day run-in period (2 days of KETO-base supplement and 2 days of placebo) before randomization. Only those able to tolerate side-effects will be included in the study. In case of unacceptable side-effects during the study period, doses will be reduced step-wise until reaching no – or accepted level of side-effects. Blood samples for determination of K^+ , Na^+ , Ca^{2+} and Mg^{2+} will be drawn after two- four days of treatment and 1-2 weeks later during the study period in the first 6 patients in the KETO-CHF study. If deemed necessary by the investigators this procedure will be carried out in the remaining 14 patients as well.

Potential benefits for the participants

Participants will potentially benefit from the 3-OHB supplement applied in this study. Participants with HFrEF will be evaluated for their present cardiac status. The right sided heart catherization is the gold standard to obtain measures of cardiac output and importantly cardiac filling pressures (preload) conditions. During daily practice, HFrEF patients often have their heart failure medication adjusted after right sided heart catherization as non-invasive assessment of preload conditions are often very difficult or impossible to obtain. Thus, each HFrEF participant will benefit by having their heart failure and diuretic treatment re-evaluated and eventually adjusted or intensified. Furthermore, the study could contribute with pivotal information on a potential future treatment of patients suffering from HFrEF, and determine whether a clinical trial of long-term hyperketonaemia should be initiated.

10 Ethical considerations

The project will be carried out in accordance with the principles of the Helsinki Declaration II. The protocol, including the written participant information and consent forms, must be finally approved by the Research Ethics Committee of the Central Denmark Region and the Danish Data Protection Agency. Data obtained from the subjects are protected under the Act concerning the processing of personal data and health law. The study will be conducted according to the Good Clinical Practice guidelines and will be reported to clinicaltrials.gov before initiation. The study does not need approval from the Danish Medicines Agency since the patients do not receive a drug but a dietary intervention (LMST journal number: 2018110888).

Based on the previously mentioned literature, the overall risk of side effects when participating in these studies is estimated to be relatively low. The results of these studies will contribute with new and essential knowledge of HFrEF and potentially new treatment approaches. Therefore, the investigators are convinced that the possible risks and side effects are outweighed by the expected benefits from the conduct of this study.

11 Collaborators and feasibility

[name] [name] ([name]) is already trained in echocardiography and management of acute and chronic HF. [name] will be trained in imaging techniques needed for the study by the

Original protocol title: *Modulation of circulating levels of the ketone body 3-hydroxybutyrate in patients with chronic heart failure: Cardiovascular and metabolic effects*

[name], Læge, PhD-studerende, Afd. for Hjertesygdomme, Aarhus Universitetshospital Skejby, Aarhus, Denmark

Scientific Committee ref.: 1-10-72-362-18

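### On the printed inputs a paired t-test needs 9 completers, not 8, for 90% power in the metabolic substudy; the 10 enrolled can lose one patient, not two

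*Combined protocol and SAP*

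**What the plan says.** The calculation is in Section 6 (Power calculation and statistics) of the combined protocol and SAP.

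- **Inputs.** For the metabolic studies, "previous studies have shown an SD of the difference of 8% and an effect size of 10" percent.
- **Power and level.** These are carried over from the preceding paragraph, where the cardiac output calculations are made "with a power of 90% and a two-sided significance level of 5" percent.
- **Result.** "With power and significance level as described above a sample size of 8 patients are needed".
- **Allowance for losses.** "To allow 20% missing values 10 patients will be included in the metabolic studies".
- **Analysis.** Under Reporting of endpoints, the same section says "Differences will be compared by appropriate paired statistical tests" and "Non-parametric statistics and appropriate log-transformation will be performed if assumption of normality is not met". It repeats the level: "A two-tailed p value of 0.05 or less will be considered statistically significant".

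Neither the power paragraph nor the analysis paragraph names a specific test or gives a sample size formula.

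**The concern.** The standardised effect is large (10/8 = 1.25), so the required number is very small. At that size the choice between a normal and a t reference distribution changes the answer by more than one patient. The printed 8 matches neither: the normal approximation gives 7 and the paired t-test gives 9.

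What is at stake is the claim about losses. A reader of Section 6 would conclude that two of the ten patients can be lost with 90% power intact. If only one can, the stated margin is overstated. This substudy involves tracer infusions, a clamp and two muscle biopsies on each metabolic day, and Section 9 bars patients on oral anticoagulants from biopsy. Incomplete data are therefore a realistic prospect.

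**Working it through.** **Inputs (all from Section 6):** SD of the within-patient difference 8%; mean difference 10%; two-sided α = 0.05; power 90%; 10 enrolled, 20% missing, so 8 completers. Standardised effect d = 10/8 = 1.25. The paired t-test is an assumption, because no test is named.

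**1. Trying to reproduce the 8.**

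- Normal approximation: n = ((1.960 + 1.282)/1.25)² = 6.72, so 7. It credits 8 patients with 94.2% power.
- Normal approximation with the small-sample term z²/2: 6.72 + 1.960²/2 = 6.72 + 1.92 = 8.65, so 9.
- Paired t-test, two-sided 5%, 90% power: 9 (step 2).
- Paired t-test, two-sided 5%, **80%** power: 8 (7 gives 78.6%, 8 gives 85.6%).
- Paired t-test, **one-sided** 5%, 90% power: 8 (7 gives 89.7%, 8 gives 93.6%).

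The two routes that return exactly 8 each contradict a printed setting, the power or the sidedness. Nothing in the document shows that either was used.

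**2. Power of the two-sided paired t-test.** Power = P(|T| > t₀.₉₇₅,ₙ₋₁), where T is noncentral t with n − 1 degrees of freedom and noncentrality 1.25√n.

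| Completers | df | Critical t | Noncentrality | Power | Difference detectable at 90% power (SD 8%) |
|---|---|---|---|---|---|
| 7 | 6 | 2.447 | 3.307 | 78.6% | – |
| 8 | 7 | 2.365 | 3.536 | 85.6% | 10.7% |
| 9 | 8 | 2.306 | 3.750 | 90.6% | 9.9% |
| 10 | 9 | 2.262 | 3.953 | 93.9% | 9.2% |

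Simulation of the t-test with 500,000 trials per row agrees: 85.8%, 90.6% and 93.9% at 8, 9 and 10.

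**3. Allowance for losses.** 8/(1 − 0.2) = 10, which matches the plan. Starting from 9, the same rule gives 9/(1 − 0.2) = 11.25, so 12. With 10 enrolled, power is 93.9% with no loss, 90.6% with one and 85.6% with two. At two losses the type II error is 14.4% instead of 10%.

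**4. Sensitivity to rounding of the inputs (8 completers, paired t-test).**

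| SD | Effect | Power |
|---|---|---|
| 7.5% | 10.5% | 92.2% |
| 7.5% | 10% | 89.6% |
| 8% | 10% | 85.6% |
| 8.5% | 9.5% | 77% |

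With the effect held at 10%, 8 completers reach 90% only if the SD is at most 7.45%, which would not round to 8%.

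**5. Sensitivity to the analysis.**

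| Analysis | 8 completers | 9 | 10 |
|---|---|---|---|
| Paired t-test | 85.6% | 90.6% | 93.9% |
| Crossover model with a period term (df = n − 2) | 83.6% | 89.3% | 93.2% |
| Exact signed-rank test (simulated, normal differences) | 80% | 86% | 93% |

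On a log scale, 8 completers give 82% to 89%, depending on how the percentages are converted. No two-sided analysis tried reaches 90% at 8, apart from the normal approximation.

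**The case against.** The strongest reply is that the error exists only relative to a method the plan does not name. The printed 8 lies one patient from the normal approximation and one from the paired t-test. The inputs are rounded figures from unidentified earlier studies, for an endpoint that is not specified, and rounding alone moves power at 8 completers between 77% and 92%. One-patient precision means little on such inputs. Missing values may also differ by endpoint (tracer, clamp, biopsy) rather than removing whole patients. Nothing in the conduct of the trial would change.

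Most of this stands as a limit on importance. The finding is conditional on a paired t-test with the inputs as printed, and rounding neither confirms nor excludes the 8. It does not restore the claim as written. The normal approximation treats the SD as known and is too optimistic with 7 degrees of freedom. The other paired analyses give less power at 8 than the paired t-test does. Most of the rounding range stays below 90%, and reaching 90% needs a larger effect as well as a smaller SD.

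The reassurance about one loss is conditional too. Nine completers hold 90% under the simple paired t-test, but give 89.3% with a period term and about 86% with the signed-rank test. That is a further reason to name the test.

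**Conclusion.** The concern holds. With an SD of 8%, a difference of 10%, a two-sided 5% level and a paired t-test, 90% power needs 9 completers. The 8 that the plan relies on give 85.6%, a shortfall of 4.4 points, and could detect 10.7% rather than 10% with 90% power. The 10 enrolled keep 90% after one loss but not after two.

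The conclusion assumes that the paired t-test was intended, that the printed inputs are used as they stand, and that a missing value removes that patient's pair from the analysis. It is minor: one completer, in a substudy, and only if the whole allowance is used. The cardiac output primary endpoint is unaffected.

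**What to change.** Keep 10 enrolled and amend the metabolic paragraph of Section 6 to name the test and state what the numbers support, for example: *Based on a two-sided paired t-test at the 5% level, 8 completers give about 86% power for a 10% difference (90% for 10.7%); 9 completers are needed for 90%.*

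If unrounded inputs or another method produced 8, print those instead. The sponsor should also confirm that the calculation used 90% power and a two-sided level, since a paired t-test returns exactly 8 at 80% power or with a one-sided 5% level.

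The cost is one sentence, with no extra patients and no change to endpoints, visits or analysis. Should the sponsor prefer to guarantee 90% power after 20% missing values, the plan's own inflation rule gives 12 enrolled; for a gap this small, restating the power is enough.
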